6.1.1 ADVERSE EVENT SEVERITY GRADES

The Investigator is responsible for evaluating all AEs and determining the severity of the event. Severity will be categorized according to the following definitions:

- Mild: Event may be noticeable to subject; does not influence daily activities; usually does not require intervention.
- Moderate: Event may be of sufficient severity to make subject uncomfortable; performance of daily activities may be influenced; intervention may be needed.
- Severe: Event may cause severe discomfort; usually interferes with daily activities; subject may not be able to continue in the study; treatment or other intervention usually needed.

The Investigator will follow all subjects who experience AEs until there is a return to the subject's baseline condition or until a clinically satisfactory resolution is achieved or the subject is lost to follow-up.

6.1.2 INVESTIGATIONAL PRODUCT CAUSALITY

Relationship of an AE to investigational product will be assessed as follows:

- Definite: There is a clinically plausible time sequence between the onset of the AE and the application of investigational product; when the event responds to withdrawal of investigational product and recurs with re-administration of investigational product.
- Probable: There is a clinically plausible time sequence between the onset of the AE and the application of investigational product; the AE is unlikely to be caused by the concurrent/underlying illness, other drugs or procedures.
- Possible: There may or may not be a clinically plausible time sequence between the onset of the AE and the application of investigational product and a cause cannot be ruled out.

• Unlikely: There is no reasonable temporal association between the test material and the suspected event and the event could have been produced by the subject's clinical state or other modes of therapy administered to the Subject.

• Unrelated: This term should be reserved for those events that cannot be even remotely related to study participation.

6.2 REPORTING ADVERSE EVENTS

For the purpose of AE reporting the trial period is defined as the period after the subject signs the informed consent/assent to the end of subject's last visit.

The Investigator will assess subjects at each scheduled study visit for the occurrence of AEs. In order to avoid bias in eliciting AEs, subjects should be asked the following non-leading question: "How have you felt since your last visit?" All AEs (serious and non-serious) reported by the subject must be recorded on the subject's study record and entered into the study database.

In addition, Chiltern must be notified within 24 hours of the Investigator's knowledge of the event by telephone or email of any immediately reportable events according to the procedure outlined below. Special attention should be paid to recording hospitalizations and concomitant therapies and medications.

6.3 IMMEDIATELY REPORTABLE EVENTS

Serious adverse events (SAEs) are considered immediately reportable events. Any SAE, whether deemed drug-related or not, must be reported to Chiltern telephone, fax, or email as soon as possible after the Investigator or coordinator has become aware of its occurrence. The Investigator/coordinator must complete a Serious Adverse Event (SAE) Form and email it to Chiltern within 24 hours of notification of the event. When appropriate, Novan will notify the appropriate regulatory body of drug related Serious Adverse Events.

Serious Adverse Event (SAE) and Safety Contact Information:

Phone: SAE Hotline: [name] ([name])

Email: [contact]

[contact]

If a subject experiences an SAE or pregnancy the Investigator must:

- 1. Report the SAE or pregnancy by telephone, fax, or email immediately (within 24 hours) after the Investigator becomes aware of the event.
- 2. Complete an SAE or Pregnancy Notification Form and email, fax, or overnight courier to Chiltern within 24 hours of knowledge of the event.

- 3. Obtain and maintain all pertinent medical records, information and medical judgments of medical personnel who assisted in subject's treatment and follow-up and document as appropriate.
- 4. Provide a more detailed report to both Chiltern and the IRB, if applicable, no later than seven days after the Investigator discovers the event as further information becomes available, and when necessary update the information with follow-up information including outcomes. This report should include a statement as to whether the event was or was not related to the use of investigational product.
- 5. The Investigator will notify the IRB of the SAE or pregnancy according to specific IRB requirements.
- 6. The Investigator will collect information on SAEs until the subject's health has returned to baseline status, until all parameters have returned to normal, or remaining health issues have otherwise been explained.

6.4 PREGNANCY

Women of child-bearing potential (WOCBP) must use an effective method of birth control during the course of the study and for 30 days following their final study visit. Allowable methods of birth control include stabilized on oral contraceptive for at least three months (90 days), IUD, condom with spermicide, diaphragm with spermicide, implant, NuvaRing®, injection, transdermal patch or abstinence with a documented second acceptable method of birth control should the subject become sexually active. Females taking hormonal contraceptives must have taken the same type for at least three months (90 days) prior to entering the study and must not change type during the study. Those who have used birth control pills or hormonal contraception in the past and stopped must have discontinued usage at least three months (90 days) prior to the start of the study.

A female is considered to be of childbearing potential unless she is post-menopausal (no menses for 24 consecutive months), surgically sterilized, or without a uterus and/or both ovaries. Premenarchal females are considered to be of childbearing potential.

Before enrolling any subject in this clinical trial, the Investigator must review guidelines about study participation including the topics below:

- Informed consent document
- Pregnancy prevention information
- Risks to unborn child(ren)
- Any drug interactions with hormonal contraceptives
- Contraceptives in current use

• Guidelines for the follow-up of a reported pregnancy

Prior to study enrollment, all subjects must be advised of the importance of avoiding pregnancy during participation in this clinical study and the potential risk factors for an unintentional pregnancy. The subject must sign an informed consent document stating that the above-mentioned risk factors and the consequences were discussed.

During the study, WOCBP should be instructed to contact the Investigator immediately if they suspect they might be pregnant (e.g., missed or late menstrual cycle). The Investigator must immediately notify Chiltern of any female subject who becomes pregnant any time during study participation, record the information on the Pregnancy Notification Form and email/fax the form to Chiltern. Subjects found to be pregnant prior to Week 40 will be discontinued from the study. Chiltern will ask the site to follow-up with the subject periodically during the pregnancy for ongoing health and safety information through term, as applicable. Protocol-required procedures for the Week 40/ET evaluation must be performed for the subject.

6.5 FOLLOW-UP OF ADVERSE EVENTS

6.5.1 FOLLOW-UP OF NON-SERIOUS ADVERSE EVENTS

Non-serious AEs that are not resolved at the time of the last scheduled study visit (Week 40/ET) must be recorded in the study database as ongoing/not recovered/not resolved.

6.5.2 FOLLOW-UP OF POST STUDY SERIOUS ADVERSE EVENTS

Serious adverse events that are identified on the last scheduled contact (Week 40/ET) must be recorded in the study database and reported to Chiltern according to the reporting procedures outlined in Sections 6.2 and 6.3. This may include unresolved previously reported SAEs, or new SAEs. The Investigator should follow these SAEs until the events are resolved, or the subject is lost to follow-up. The Investigator should continue to report any significant follow-up information to Chiltern and the IRB up to the point the event has been resolved. Resolution means the subject has returned to the baseline state of health, or the Investigator does not expect any further improvement or worsening of the subject's condition.

Any new SAEs reported by the subject to the Investigator that occur after the last scheduled contact and are determined by the Investigator to be reasonably associated with the application of investigational product should be reported to Chiltern and the IRB.

6.6 OVERDOSAGE

There is no specific antidote for nitric oxide. In the event of an overdose, best supportive care should be utilized. Methylene blue may be used to treat subjects exhibiting methemoglobinemia.

6.7 DISCONTINUATION OF INDIVIDUAL SUBJECTS FROM THE STUDY

Subjects who develop intolerance to the product as defined by scores of 3 (severe) on 2 or more categories of tolerability (erythema, scaling, dryness, pruritus, burning/stinging) shall be discontinued from the study.

If a subject is determined to be pregnant prior to Week 40, the subject will be discontinued from the study but followed until term.

7. STATISTICAL ANALYSIS

7.1 GENERAL CONSIDERATIONS

All statistical processing will be performed using SAS® unless otherwise stated. A detailed description of the statistical methodology and data reporting for this study will be provided in the Statistical Analysis Plan (SAP). The SAP will be finalized before the database is locked and released to Novan. Any deviations from the SAP will be justified in the clinical study report.

7.2 POPULATIONS

7.2.1 SAFETY POPULATION

The safety population will include all subjects that have been dispensed study drug.

7.3 DEMOGRAPHIC AND BASELINE CHARACTERISTICS

Subject demographic and baseline characteristics will be summarized. For continuous variables (e.g., age), mean, median, standard deviation, minimum and maximum will be presented. Categorical variables (e.g., ethnicity, race) will be summarized with frequency count and percentage.

7.4 DESCRIPTIVE STATISTICS

Safety data will be summarized as indicated below for the safety population.

Continuous data will be summarized with sample size (N), mean, median, standard deviation, minimum and maximum. Categorical data will be summarized with N, frequency counts, and percentages of N.

7.5 SAFETY

7.5.1 ADVERSE EVENTS

All AEs that occur during the study or continue after enrollment into this study will be recorded and classified on the basis of MedDRA terminology. Treatment-emergent adverse events (TEAEs) are defined as AEs reported on or after the first day of enrollment in this long term safety study.

All information pertaining to an AE noted during the study will be listed by subject, detailing verbatim term given by the PI or designee, preferred term, system organ class (SOC), onset date, resolution date, severity, seriousness, action taken, outcome, and drug relatedness. The event onset will also be shown relative (in number of days) to date of first dose in this study.

Treatment-emergent AEs will be summarized by the number of subjects reporting a TEAE, SOC, preferred term, severity, relationship to study drug (causality), and seriousness. When summarizing AEs by severity and relationship, each subject will be counted only once within a system organ class or a preferred term by using the event with the highest severity and greatest relationship within each classification.

Adverse events will also be summarized by windows of exposure to study drug. The windows will include but are not limited to: 1) within the first 24 hours of exposure, 2) up to 1 month of exposure, 3) up to 3 months of exposure, 4) up to 6 months of exposure and 5) up to 12 months of exposure.

AEs will also be summarized based on extent of exposure as described in Section 7.7

Serious AEs will be summarized by severity, and relationship to study drug, and individual SAEs will be listed by subject. In addition, a list of subjects who prematurely discontinue from the study due to an AE will be provided.

7.5.2 PHYSICAL EXAMINATION

Any clinically significant changes from Baseline will be documented as an AE.

7.5.3 VITAL SIGNS

Blood pressure and pulse will be summarized from Baseline through Week 40. Additionally, change from Baseline in vital signs will be summarized at Week 4, 12, 24, 36, and 40. Clinically significant changes from Baseline will be documented as an AE.

7.5.4 URINE PREGNANCY TESTS

Urine pregnancy tests results for WOCBP will be presented in data listings by subject.

7.6 TOLERABILITY

Distribution and shift in cutaneous tolerability assessments (erythema, scaling, dryness, pruritus, burning/stinging) will be summarized from Baseline to Week 40.

7.7 EXTENT OF EXPOSURE

Extent of exposure will be based on days of treatment and the body surface area treated (face, upper back, and/or upper chest/shoulders) as collected at each visit for each subject. AEs will also be summarized by extent of exposure to determine if there is a safety signal due to duration of exposure or total body area exposed.

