7.9 SAMPLE SIZE AND POWER CONSIDERATIONS

Approximately 600 subjects who completed treatment in either the NI-AC301 or NI-AC302 will be enrolled into the study from approximately 100 sites in North America. The main objective of this study is to evaluate the long term safety of SB204, therefore, no sample size or power calculations were performed.

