### 3.6 Sample Size

The main objective of this study is to evaluate the long term safety of SB204, therefore, no sample size or power calculations were performed.

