## 4 Statistical Methodology

#### 4.1 Planned Analyses

All statistical processing will be performed using statistical analysis software (SAS®) unless otherwise stated. Safety analyses will be performed using the safety population.

Continuous data will be summarized with sample size (N), mean, median, standard deviation, minimum and maximum. Categorical data will be summarized with N, frequency counts, and percentages, based on N.

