#### 4.5 Safety

#### 4.5.1 Adverse Events

All AEs that occur during the study or continue after enrollment into this study will be recorded and classified on the basis of Medical Dictionary for Regulatory Activities (MedDRA) terminology version 18.1. Adverse events ongoing at end of the pivotal study will be carried forward to this study, will not be considered treatment-emergent for this study, and will be summarized separately by SOC, PT, and relatedness. Treatment-emergent AEs (TEAEs) will be defined as AEs reported on or after the first day of enrollment in this long term safety study.

All information pertaining to an AE noted during the study will be listed by subject, detailing verbatim term given by the Investigator or designee, preferred term, system organ class (SOC), onset date, resolution date, severity, seriousness, action taken, outcome, and drug relatedness. The event onset will also be shown relative (in number of days) to date of first dose in this study.

Treatment-emergent AEs will be summarized by the number of subjects reporting a TEAE, SOC, preferred term, severity, relationship to study drug (causality), and seriousness. When summarizing AEs by severity and relationship, each subject will be counted only once, within a system organ class or a preferred term, by using the event with the highest severity and greatest relationship within each classification.

Serious AEs will be summarized by severity, and relationship to study drug, and individual SAEs will be listed by subject. In addition, a list of subjects who prematurely discontinue study drug due to an AE, had AEs leading to treatment modification, and AEs that resulted in death will be provided.

Adverse events will also be summarized by windows of duration of exposure to study drug to determine if there is a safety signal due to duration of exposure. The windows of exposure will include but are not limited to: 1) within the first 24 hours (i.e. Day 1 of the LTS study), 2) up to 1 month (i.e. 2-30 days), 3) up to 3 months (i.e. 31-90 days), 4) up to 6 months (i.e. 91-180 days) and 5) up to 12 months (i.e. 181-365 days).

Adverse event incidence will also be summarized by the extent of exposure categories (in grams) as described in section 4.4.

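### The AE-by-exposure summaries are meant to settle whether there is a safety signal but carry no confidence interval, so a flat or zero row does not show what risk was excluded

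*Protocol*

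**What the plan says.** Protocol 7.7 (Extent of Exposure) gives the summaries of AEs by exposure a purpose: "to determine if there is a safety signal due to duration of exposure or total body area exposed". SAP 4.5.1 (Adverse Events) attaches a narrower form to the duration windows only: "to determine if there is a safety signal due to duration of exposure". For the gram categories it states no such purpose: "Adverse event incidence will also be summarized by the extent of exposure categories (in grams) as described in section 4.4".

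The planned statistics are in Protocol 7.4, "Categorical data will be summarized with N, frequency counts, and percentages of N", and SAP 4.1, "Categorical data will be summarized with N, frequency counts, and percentages, based on N". The shells for Tables 14.3.3.1, 14.3.3.2.1 and 14.3.3.2.2 show subjects with a percentage and numbers of events. I found no confidence interval, upper bound, trend estimate, test or signal criterion for any AE rate in either document.

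On size, Protocol 7.9 says: "Approximately 600 subjects who completed treatment in either the NI-AC301 or NI-AC302 will be enrolled into the study". It adds that "no sample size or power calculations were performed", and SAP 3.6 says the same. SAP 4.4 would first consider quartiles for the gram categories, while the shells print cuts at 100, 330 and 675 g.

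**The concern.** Safety is the only primary objective. The wording promises a determination, yet nothing planned conveys precision. If a row is flat across columns, or empty, the report can say that nothing was noticed. It cannot say how large a risk, or how large an increase with exposure, the data rule out.

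This matters most for uncommon and serious events. There, small counts make similar percentages likely even when the underlying risks differ, and a zero is easily read as safe. With no sample-size reasoning behind the 600, an interval is the one simple device that would tell the reader what the data exclude.

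**Working it through.** **The plan's own figures.** There is no power or precision calculation to reproduce. The worked gram examples in SAP 4.4 do reproduce: 200 × 0.9 = 180 g and (100 + 50) × 0.9 = 135 g.

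**Inputs.**
- Total: about 600 (Protocol 7.9).
- Gram column size: 600/4 = 150. This is an assumption based on the quartile remark in SAP 4.4; column sizes under the shells' fixed cuts are unknown.
- Reference AE rates: not in the documents; I assume 1% to 20%.
- Two-sided 5% level, 80% power and a doubling of risk: my yardsticks, not the plan's.
- No dropout, for simplicity. Protocol 4.1.4 says withdrawals are not replaced, so real numbers will be lower.

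**Zero events.** The exact two-sided 95% upper limit is 1 − 0.025^(1/n).
- n = 600: 1 − 0.025^(1/600) = 0.61%.
- n = 150: 1 − 0.025^(1/150) = 2.4%.

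An event with a true risk of 0.2% is seen in nobody among 600 with probability 0.998^600 = 0.30.

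**Power for a doubling, 150 against 150.** For the pooled test, power = Φ{[(p2 − p1)√n − 1.96√(2p̄(1 − p̄))] / √(p1(1 − p1) + p2(1 − p2))}. At 5% against 10% this is Φ{(0.612 − 0.730)/0.371} = Φ(−0.317) = 37%.

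| Rates | Pooled test | Fisher exact |
|---|---|---|
| 1% v 2% | 11% | 2% |
| 2% v 4% | 17% | 9% |
| 5% v 10% | 37% | 30% |
| 10% v 20% | 68% | 63% |
| 12% v 24% | 78% | not run |
| 13% v 26% | 81% | not run |
| 20% v 40% | 97% | 96% |

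The pooled test reaches 80% power at a reference rate of about 12.7%. With other column sizes the threshold moves: about 21% with 75 per column and 7% with 300.

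**What equal percentages exclude.** For a events in each of two columns of 150, the 95% CI for a risk ratio of 1 is exp{±1.96√(2/a − 2/150)}:
- 3 v 3 (2%): 0.21 to 4.9
- 8 v 8 (5.3%): 0.39 to 2.6
- 15 v 15 (10%): 0.51 to 1.97
- 30 v 30 (20%): 0.64 to 1.57

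Identical percentages therefore fail to exclude a doubling until the rate is about 10%.

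**Duration windows.** These do not divide the 600. The same subjects pass through successive windows, so on the timing in the SAP text a window can hold up to about 600 less dropouts. Treating two windows of 600 as independent samples, which is only an approximation, power for a doubling is 91% from 5% but 30% from 1%. The footnote to Table 14.3.3.2.1 instead starts the clock at first SB204 dose, possibly in the pivotal study. The early windows would then hold mainly SB204-naïve subjects, whose number is not given.

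**What an interval would show in a column of 150.** Clopper-Pearson 95%: 3/150 = 2.0% (0.4% to 5.7%); 8/150 = 5.3% (2.3% to 10.2%); 15/150 = 10% (5.7% to 16.0%).

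**The case against.** The study is openly descriptive and unpowered. A reader might infer two stronger charges, and the documents support neither.

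- *The columns are too small to show a doubling of risk.* Not without a rate attached: at 20% against 40% power is 96–97%. The figure of 150 is itself an assumption, and duration windows can be much larger. The SAP states the signal purpose only for those windows. Even at 150 per column, a true doubling gives a higher observed percentage in the right column about 80% of the time at 2% against 4%, and about 99% at 10% against 20%.
- *The trial will declare no signal from similar percentages.* Neither document states such a rule. Percentages are also not the only material. The shells give event counts, separate tables for related, serious, fatal, treatment-modifying and discontinuation-related TEAEs, and severity tables. Listing 16.2.8.1 gives duration and extent of exposure for each event, and there are tolerability and vital-sign summaries.

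Both corrections stand, as does the remark that power describes a test nobody planned. It is used here only as a yardstick. It is also true that a reader with count and denominator could compute an interval.

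What remains is that the plan states a determination and reports no precision for any AE rate. An interval is itself a descriptive statistic, so the descriptive nature of the study is no reason to omit it.

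**Conclusion.** The point holds as a reporting gap. The stated purpose goes beyond what counts and percentages can deliver, because a flat or zero row does not show what risk was excluded. The firmest figures are the zero-event limits: 0.61% for 0/600 and 2.4% for 0/150. They depend only on the denominators.

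The statement on doubling is conditional. It assumes gram columns of about 150, no dropout, a two-sided 5% comparison and assumed AE rates. Under those conditions power is below 80% for reference rates under about 12–13%, and high for common events. It does not carry over to the duration windows. Nothing here calls for more subjects.

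**What to change.** 1. In SAP 4.5.1 and the shells for Tables 14.3.3.1, 14.3.3.2.1 and 14.3.3.2.2 and their repeats, add exact (Clopper-Pearson) 95% intervals for four rows: any TEAE, related TEAE, TEAE leading to discontinuation, and serious TEAE. Give them overall, by SB204 experienced and naïve where shown, and per exposure column.
2. Use the number of subjects at risk in each column as the denominator, and say so in the footnote.
3. Report the upper limit for zero counts too.
4. Replace the signal-determination wording by a statement that AE incidence will be described by exposure, with the upper confidence limit. Align Protocol 7.7 at its next amendment, or state in the SAP that this is how it is read.

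Do not add a highest-minus-lowest gram-column difference. Cumulative grams are a post-baseline quantity: a subject who stops early for an AE accumulates fewer and, if columns use final totals, falls into a low column. Grams also mix area with days. About 100 g is 111 face-only days (100/0.9) or 28 days on four areas (100/3.6), so the contrast would not isolate body area. The per-column intervals should likewise not be read as a dose-response.

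Cost: four rows over five windows, four gram columns and overall is 4 × 10 = 40 intervals, plus 4 × 2 = 8 by prior treatment. They would be unadjusted for multiplicity and should be labelled so. No new data or subjects are needed. The downside is a less favourable-looking safety statement.
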